7.1 Definitions

Adverse Event

Adverse events (AE) and Serious Adverse Events (SAE) will use the descriptions and grading scales found in the revised **NCI Common Terminology Criteria for Adverse Events (CTCAE)**. This study will utilize the CTCAE v5.0 for adverse event reporting. All appropriate treatment areas will have access to a copy of the CTCAE v5.0 and adverse events will only be collected up until 30 calendar days after completion of the injection. Any AE's which remain unresolved at 30 days post-injection will be assessed for resolution at subsequent standard of care follow-up visits. Intercurrent illnesses or

injuries should be regarded as adverse events. Abnormal results of diagnostic procedures are considered to be adverse events if the abnormality:

- results in study withdrawal
- is associated with a Serious Adverse Event (SAE)
- is associated with clinical signs or symptoms
- leads to additional treatment or to further diagnostic tests
- is considered by the investigator to be of clinical significance

AEs Not to Include:

- Medical or surgical procedures (e.g. endoscopy, appendectomy); the condition that leads to the procedures is an AE
- Situations where an untoward medical occurrence did not occur (elective and/or convenience admission to hospital)
- Anticipated day-to-day fluctuation of pre-existing disease(s) or condition(s) present or detectable at the start of the study that do not worsen in grade or severity.
- The disease/disorder being studied, or expected progression, signs, or symptoms of the disease/disorder being studied, unless more severe than expected for the subject's condition.
- Grade 1 adverse events that are expected and related for radiotherapy and chemotherapy, if indicated (listed in the radiation and chemotherapy protocol/consent).
- Abnormal lab values
- Adverse events in patients receiving chemotherapy or radiation therapy for metastasis and/or additional cancers will not be collected.

7.2 *Expedited Adverse Event Reporting*

Common Toxicity Criteria

Toxicity will be evaluated with the NCI Common Toxicity Criteria (CTCAE) v. 5.0.

Serious Adverse Events

A SAE is defined as any of the following:

- Fatal or life-threatening (real risk of dying) event
- Requires or prolongs hospitalization
- Causes persistent or significant disability/incapacity
- Results in a birth defect or congenital anomaly
- Causes cancer

All hospitalizations or prolongation of existing hospitalization for medical events regardless of phase of study, expected or unexpected attributions are SAE's.

Serious, unexpected drug-related adverse events will be reported to the University of Pennsylvania IRB, and the University of Pennsylvania Cancer Center Data and Safety Monitoring Committee (DSMC) using the expedited reporting guidelines as is required by each board.

The toxicities that develop during the standard chemotherapy portion of this trial will not require reporting in an expedited manner.

7.3 *Lidocaine Safety and Adverse Reactions*

The clinical adverse event profile, pharmacokinetics, pharmacodynamics, and toxicology for injectable lidocaine is well-established and readily available from the manufacturer(s) (<https://dailymed.nlm.nih.gov/dailymed/fda/fdaDrugXsl.cfm?setid=76176d50-a987-c9f9-e053-2991aa0aea0f&type=display>). Lidocaine is one of the most commonly used local anesthetics with well-established safety data for its use as an anesthetic but does not have proven safety data for use as a cancer therapy. The most common side effects of lidocaine injection are swelling, bruising, or soreness at the injection site, and temporary rapid heartbeat. Lidocaine overdose can cause central nervous system (CNS) effects such as confusion, seizure, or unconsciousness, respiratory depression and/or respiratory arrest, and cardiovascular effects such as cardiac arrhythmias. Reactions to lidocaine may result from intra-arterial injection of lidocaine with retrograde flow to the cerebral circulation. Less common side effects include damage to nerves resulting in temporary or possibly permanent numbness or tingling and severe and possibly life-threatening allergic reactions.

Monitoring and Management of Adverse Events

Participants will be closely monitored for any adverse events, particularly those potentially related to lidocaine administration. As defined above, the total injected volume of lidocaine will not exceed the established maximum tolerated dose, minimizing the risk to participants. The following precautions and monitoring procedures will also be implemented:

Intraoperative and Postoperative Monitoring:

- In accordance with our standard of care peri-operative management, all participants will undergo continuous electrocardiographic (ECG) monitoring during surgery and immediately postoperatively to detect any arrhythmias or other cardiovascular events.
- Vital signs, including heart rate, blood pressure, and oxygen saturation, will be recorded at regular intervals throughout the procedure and in the recovery period.

- Participants will be monitored in the recovery area for at least 1-hour post-injection, with extended monitoring if signs of toxicity are noted.

Management of Specific Adverse Events:

- **Arrhythmias:** Anti-arrhythmic medications and defibrillators are readily available in the operating room and recovery areas. Any significant arrhythmias will be managed according to our standard clinical protocols, including potential transfer to an intensive care unit if needed.
- **Lidocaine Central Nervous System Toxicity:** CNS toxicity will be managed with supportive measures, including supplemental oxygen, and antiepileptics, per our standard clinical protocols. If required, intravenous lipid emulsion (ILE) therapy, the established treatment for severe local anesthetic systemic toxicity, will be administered. Airway protection, including intubation, will be provided if necessary.
- **Hypersensitivity and Allergic Reactions:** Epinephrine, antihistamines, and corticosteroids will be available in the perioperative period to treat any severe allergic reactions.

This monitoring and management plan will ensure that any adverse reactions are identified and treated promptly, thereby minimizing risks to participants.

7.4 *Dose-Limiting Toxicities and Stopping Rules*

Dose-limiting toxicities (DLTs) will be defined as any of the following adverse events occurring after intratumoral lidocaine injection:

- **Grade 3 or higher cardiac arrhythmia, seizure, or other central nervous system toxicity** attributed to lidocaine, as graded according to the NCI Common Terminology Criteria for Adverse Events (CTCAE) Version 5.0.
- **Any other Grade 3 or higher adverse event** directly attributed to lidocaine that, in the judgment of the Medical Monitor and Study Sponsor, poses a significant risk to participant safety.

Stopping Rules for Safety

A stopping rule for safety will halt accrual to the study if risks to subjects unexpectedly outweigh the benefits due to unexpected severe adverse events (SAEs). This determination will be made by the DSMC, Medical Monitor, and Study Sponsor. The specific stopping rules are as follows:

- **Cohort-Based Pausing:** If 2 or more participants within a cohort of 5 experience DLTs, the study will be paused. An independent safety review will be conducted by the DSMC and Medical Monitor. The study will only resume if the DSMC concludes it is safe to proceed.

- **Overall Study Pausing:** If **more than 10% of participants across the study experience a DLT or Grade 3 or higher adverse event related to lidocaine**, the study will be paused. The DSMC, Medical Monitor, and Study Sponsor will re-evaluate the safety profile of intratumoral lidocaine injection to determine if modifications to the protocol or dosing are required or if the study should be permanently discontinued.

Reporting and Adjustments

Any unexpected SAEs will be reported to the IRB promptly, and study procedures will be adjusted as necessary to mitigate further risk.

8 Data Handling and Record Keeping

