3.1 General Design

This is a phase I patient-blinded, randomized controlled trial evaluating intratumoral lidocaine injection prior to definitive surgery in HPV associated OPSCC. Patients with OPSCC undergoing direct laryngoscopy who are being considered for definitive TORS

and selective neck dissection, will be eligible. Patients will be randomized and blinded to intratumoral injection of 1% lidocaine (intervention arm) or no injection (control arm) at the time of direct laryngoscopy. After administration of general anesthesia and biopsy, lidocaine will be injected under direct visualization (not exceeding the maximum tolerated dose of 4.5 mg/kg body weight) into the primary tumor. The control arm will receive no injection.

Blood samples will be obtained prior to direct laryngoscopy/study intervention (pre-biopsy) and again after the intervention (post-biopsy). The pTR rate (defined above and in published literature^{78, 79}) will be determined by the designated study pathologist ([name], PhD) with head and neck expertise using increments of 10% for the biopsy and surgery specimens. The scores will be grouped as pTR-0 (<10%), pTR-1 (10%–49%), and pTR-2 (≥50%).

Patients will otherwise receive institutional standard of care treatment including TORS primary site resection, selective neck dissection, and additional indicated adjuvant radiation therapy with or without chemotherapy. All enrolled patients will be assessed for safety measured by adverse events. If a patient does not ultimately receive primary surgery following their direct laryngoscopy/study intervention (based on surgical candidacy, patient preference, or other reasons), then they will not be counted as an evaluable subject, as the primary endpoint pTR requires a surgical specimen for evaluation. If a patient is determined to have a pathology other than HPV associated OPSCC after their direct laryngoscopy, then they will not be counted as an evaluable subject.

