3.2 Primary Study Endpoints

- 1) Safety measured by occurrence of adverse events.
- 2) Pathological tumor response (pTR) in the primary tumor following surgical resection.

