An outline of the typical study visit schedule is provided below. There will be no planned additional study visits compared to routine, standard of care (SOC). Clinical research procedures are underlined in the table for clarification purposes.

Visit Number	Visit Procedures
Visit 1	Come to the clinic for a routine (SOC) clinic visit(s). Decide if you want to participate in the study, ask questions, sign the consent form if you do want to participate.
Visit 2	Have a pre-operative research blood draw with blood sample storage on the day of your direct laryngoscopy with biopsy.

	
Study Intervention: Participants will be randomly assigned to two groups.
 
 • Group 1 (Intervention Arm) – Biopsy and injection of lidocaine into tumor while you are under general anesthesia for your direct laryngoscopy. • Group 2 (Control Arm) – Biopsy without injection of lidocaine while you are under general anesthesia for your direct laryngoscopy.
Visit 3	Routine (SOC) clinic visit to discuss the results of your direct laryngoscopy with biopsy and have a research study blood draw with blood sample storage . You will also be asked to take a short survey.
Visit 4	Routine (SOC) treatment with primary surgery or primary radiation with storage of tumor tissue for research . This will allow researchers to study leftover tissue removed during your routine care.
Visit 5	Routine (SOC) follow up for cancer surveillance per National Comprehensive Cancer Network guidelines.

6 Statistical Plan

This study is considered exploratory because, to our knowledge, no prior published data exists on the effects of lidocaine injection on pathologic tumor response, survival, and recurrence in HPV associated OPSCC. The planned sample size for this phase I trial is 30 evaluable subjects split equally between the intervention and control arms. Subjects will need to have a definitive diagnosis of HPV associated OPSCC and undergo surgery (TORS and neck dissection) to be considered evaluable.

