The co-primary objectives of this study are to determine safety and if the proportion of patients with pTR-2 in the primary tumor is different in the intervention group compared to the control arm. All enrolled participants, regardless of HPV status or final pathology, will be included in the primary safety analysis. Thus, any adverse events or dose-limiting toxicities observed in participants will contribute to the overall safety assessment of intratumoral lidocaine.

For the pathologic response primary endpoint, H_0 is that there is no difference in the proportions of patients with pTR-2 between the intervention or no intervention (control) groups; H_a is that the intervention arm is associated with a higher proportion of pTR-2. The proportion of pTR-2 will be compared between the intervention and control arms using a one-sided Fisher's exact test with a significance level of 0.05. A 95% confidence interval will be used. We estimate that a sample size of 30 patients is needed to allow us to detect

with 80% power at the one-sided alpha level of 0.05 a major pathologic treatment rate of 30% in the intervention arm compared to 0% in the control arm.

In addition to hypothesis testing for the pathologic response primary outcome, we will use within-between interaction models to account for the effects of the treatment and the interaction between treatment and patient and disease factors including age, sex, disease stage, and adverse pathologic features (e.g. tumor grade, perineural invasion, lymphovascular invasion). We will estimate means and standard deviations for each group and the correlation within subjects to better understand the relationship between repeated measures. We will use mixed-effects models to handle within-subject correlations and between-subject comparisons.

The secondary endpoints include 2-year locoregional control (LCR) rates, progression-free survival (PFS), metastasis-free survival (MFS), and overall survival (OS). PFS will be defined as time from random assignment to disease progression or death from any cause. MFS will be defined as time from random assignment to first evidence of distant metastatic disease or death from any cause. OS will be defined as the time from random assignment and death due to any cause. 95% confidence intervals will be used. LRC rates, PFS, MFS, and OS will be estimated using the Kaplan–Meier method, and log-rank test will be used to compare the two groups using a significance level of 0.05.

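### Section 7.1 bars adverse-event collection for participants on chemotherapy or radiation for metastasis or another cancer, whereas Sections 3.1 and 6 count every enrolled participant's adverse events in the primary safety analysis

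*Protocol*

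**What the plan says.** Safety is the first primary endpoint. Section 3.2 defines it as "Safety measured by occurrence of adverse events".

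Three statements fix who and what counts:

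- Section 3.1: "All enrolled patients will be assessed for safety measured by adverse events".
- Section 6, on the population: "All enrolled participants, regardless of HPV status or final pathology, will be included in the primary safety analysis".
- Section 6, on the events: "any adverse events or dose-limiting toxicities observed in participants will contribute to the overall safety assessment of intratumoral lidocaine".

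Section 3.1 also foresees participants whose diagnosis changes after the injection. The sentence that opens "If a patient is determined to have a pathology other than HPV associated OPSCC after their direct laryngoscopy" makes them non-evaluable for pathologic response. Section 6 keeps them for safety.

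Section 7.1 sets the collection period: "adverse events will only be collected up until 30 calendar days after completion of the injection". Its list of adverse events not to include ends with: "Adverse events in patients receiving chemotherapy or radiation therapy for metastasis and/or additional cancers will not be collected".

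**The concern.** The last bullet of the Section 7.1 list selects patients, not events. As written, a participant who is receiving the named treatment has no adverse event recorded, whatever its cause. The bullet makes no exception for events attributed to lidocaine, for serious events or for dose-limiting toxicities. An event that is not collected cannot contribute to an analysis that is meant to take in any event from any enrolled participant.

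At stake is the first of the two co-primary questions. Section 7.3 concedes that lidocaine has no proven safety record as a cancer therapy, so a complete event record is a main product of this trial. A participant who remains in the denominator without recorded events looks the same as one who had none.

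**Working it through.** The protocol gives no figure on this point to reproduce. The check compares texts, with a short formula for the direction of the bias.

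**1. Do the rules collide?**

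| Question | Sections 3.1 and 6 | Section 7.1, last bullet |
|---|---|---|
| Which participants? | All enrolled, whatever the HPV status or final diagnosis | Drops those on chemotherapy or radiation for metastasis or an additional cancer |
| Which events? | Any adverse event or dose-limiting toxicity | None in those participants |
| Limit by attribution, grade or onset? | None | None |

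They do, for any enrolled participant who meets the bullet's description.

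**2. Could the bullet be read as covering only the other treatment's toxicity?** The text does not say so. Another bullet in the same list, on adjuvant radiotherapy and chemotherapy, is restricted to Grade 1 events that are expected and related. The list therefore contains a properly limited exclusion, and this bullet lacks the limits.

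**3. Who meets the description?**

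- *Participants under treatment for another cancer at enrolment.* On prior or concurrent cancer and its treatment, Section 4.2 excludes only previous external beam radiation to the head and neck, previous chemotherapy for head and neck cancer, and distant metastatic disease. Someone on treatment for a cancer elsewhere can be enrolled and injected. For that person the bullet covers the whole window, so even an acute non-serious reaction would go unrecorded.
- *Participants who start such treatment within 30 days of the injection,* because a second cancer or spread has been found. On the narrower reading of *receiving*, their events are lost only from the start of that treatment.

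The protocol gives no count for either group.

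**4. Direction of the bias.** Let N be the number enrolled in an arm, x the number who have an adverse event, and m the number of those whose only events are uncollected. The true proportion is x/N and the reported one is (x − m)/N. The error is −m/N, which is never positive. N is all enrolled participants, a number the protocol does not give, and m is unknown, so no percentage is put on it. The bullet applies in both arms, so the sign of any error in the difference between arms is not fixed.

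**5. The pausing rule.** Section 7.4 pauses the study when more than 10% of participants have a dose-limiting toxicity or a lidocaine-related event of Grade 3 or higher. Purely as an illustration, assume 30 participants in the denominator: 3/30 = 10.0% does not exceed the limit and 4/30 = 13.3% does. One unrecorded event matters there only if the count stands exactly at the threshold.

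**The case against.** The strongest reply is that the reach is small. Collection stops at 30 days and distant metastasis is excluded at entry. The reactions that Section 7.3 is most concerned with (arrhythmia, central nervous system toxicity, allergy) are watched for in the operating room and in recovery. For a participant who starts other treatment later, such events would normally be on record already. All of this stands and limits the effect. It does not help the participant who is already on treatment for another cancer when injected.

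A second reply is that serious events have their own route. Section 7.2 treats all hospitalizations for medical events as serious whatever their attribution. Section 9.3 has all observed serious events presented to the Medical Monitor, together with whether they invoked a stopping criterion. This also stands. A reader might infer that no event in these participants could reach the pausing rules, and that goes too far. The route is incomplete, though: Section 7.2 defines seriousness by outcome while Section 7.4 works by grade, so a Grade 3 event that meets no seriousness criterion is not assured of it.

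Three further inferences are tempting and not supported:

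- *That metastasis includes neck nodes, so that much of the trial is affected.* The same list deals separately with indicated radiotherapy and chemotherapy. That bullet would be largely empty in a node-positive population if nodal disease counted as metastasis.
- *That such participants are built into the design because Visit 4 in Section 5.7 allows* "Routine (SOC) treatment with primary surgery or primary radiation". Primary radiation there would normally treat the presenting cancer. HPV-negative oropharyngeal carcinoma is likewise the presenting cancer, not an additional one.
- *That each affected participant is worth one fifteenth of the lidocaine arm's rate.* Fifteen per arm is the evaluable target. The safety set is everyone enrolled.

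**Conclusion.** The contradiction holds as written. Section 7.1 withholds collection, by patient, from people whom Sections 3.1 and 6 count in full. Any resulting error in an arm's adverse-event rate is downward. The number affected is not given and is probably small, possibly zero, so no magnitude is claimed.

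The conclusion rests on two readings. The bullet means what it says, since no limit by attribution appears. Treatment for a cancer outside the head and neck is no bar to entry, since Section 4.2 lists none. If the bullet was meant only for toxicities of the other treatment, the intention is reasonable but the wording does not carry it. How a statistical analysis plan might handle incomplete safety follow-up does not settle the matter, because no analysis can recover events that were never collected.

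**What to change.** Reconcile Section 7.1 with Sections 3.1 and 6 by turning the bullet into an exclusion of events. Suggested content: events judged attributable solely to chemotherapy or radiation given for distant metastasis or an additional cancer are not collected; all other events in these participants are collected for the full 30-day window and enter the Section 6 safety analysis. Writing *distant* also removes the doubt over what metastasis covers.

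The cost is a one-sentence amendment, a few more adverse-event entries and an attribution judgement for each. No dose, procedure or clinical management changes.

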8.1 Records

All patients must have a signed Informed Consent Form. Confirmation of study eligibility will be completed by a participating investigator via the electronic medical record (EPIC) prior to entering the study.

Confidential research charts will be kept in locked cabinets at each participating institution. Subjects will be assigned a study number at the time of study enrollment. This study number and not the subject's name will be used on all case report forms.

HIPAA Compliance:

Prior to direct laryngoscopy and randomization to the intervention vs control, each subject will sign a study informed consent, which also includes consent acknowledging the uses and disclosures of protected health information (PHI) in this study as required by The Health Insurance Portability and Accountability Act (HIPAA). PHI will not be shared with any outside institution except as required by law. Any reporting of the results of this study will be done only with de-identified patient data. Confidentiality will be protected as outlined below.

- Each subject will sign a study informed consent electronically prior to direct laryngoscopy and randomization to the intervention vs control

